6.2 IRB approval

Documentation of IRB approval must be on file in the Registration Office before an investigator may register any patients.

In addition to submitting initial IRB approval documents, ongoing IRB approval documentation must be on file (no less than annually) at the Registration Office (fax: [REDACTED]). If the necessary documentation is not submitted in advance of attempting patient registration, the registration will not be accepted and the patient may not be enrolled in the protocol until the situation is resolved.

When the study has been permanently closed to patient enrollment, submission of annual IRB approvals to the Registration Office is no longer necessary.

6.3 Verification

Prior to accepting the registration, registration application will verify the following:

- Patient eligibility
- Existence of a signed consent form
- Existence of a signed authorization for use and disclosure of protected health information

6.4 Treatment location requirements

Treatment on this protocol must commence at Mayo Clinic Rochester under the supervision of a medical oncologist, pain specialist, or associated allied health personnel.

6.5 Start of treatment

Treatment cannot begin prior to registration and must begin ≤ 50 days after registration.

6.6 Booklets

Patient questionnaire booklet is available on site; copies are not acceptable for these submissions.

6.7 Randomization Procedures

6.71 The factors defined in Section 5.0, together with the registering membership, will be used as stratification factors.

6.72 After the patient has been registered into the study, the values of the stratification factors will be recorded, and the patient will be assigned to one of the following treatment groups using the Pocock and Simon dynamic allocation procedure which balances the marginal distributions of the stratification factors between the treatment groups.

- Scrambler Therapy
- TENS Therapy

6.8 Optional continuation - Treatment Crossover

6.81 Patient may enter crossover treatment once original 2 weeks of treatment and 8 weeks of observation are complete.

6.82 Complete Optional Crossover Continuation form.

7.0 Protocol Treatment

7.1 Treatment Schedule for Scrambler arm

7.11 Day 1- Initial treatment

7.111 The locations of symptoms will be assessed.

7.112 Pretreatment questionnaires completed

7.113 Placement of electrodes and treatment

A decision will be made by the treating person as to where electrodes should be placed, keeping in mind that the general principle regarding Scrambler Therapy is that the cutaneous EKG electrode patches, or channels, are applied above and below the area of pain/tingling if possible. The placement of the electrode pair of each channel follows the "geometry" of the pain, which in CIPN normally extends in vertical arrangement. See appendix XIII for principles of this treatment.

More specifically, the treatment is carried out using surface electrodes, two for each channel (maximum 5) of the device, depending on need. Choosing where to apply the electrodes is important. As a basic technique, the electrodes should never be applied directly on the painful area, but, ideally, should be 2-3 fingerbreadths proximal, distal, or lateral to the pain.

Treatment should be started and over about 10-30 seconds, the intensity should be increased to the maximal level that is tolerated. In doing so, the operator will ask the patient to let it be known when they feel any stimulation, then when they note any stinging feeling and then when any stinging is too uncomfortable. The goal is to have the patient at the highest tolerable setting while helping the baseline tingling and/or pain and to be below any substantial discomfort under the electrodes.

The patient should then be asked whether he/she has any residual pain/tingling in the area of focus. The goal is to reduce all pain to zero. If there is residual pain, then the operator can choose to increase intensity if possible, relocate the electrodes of the initial channel, or, if there is substantial improvement with the initial channel and pain is outside the area of the initial channel, another channel can be used to treat the residual pain/tingling area, again striving for a complete resolution of the discomfort.

If a patient develops pain or a burning sensation with any of the electrodes, then the treatment should be interrupted and the electrode should be moved farther away from the pain source. For the electrodes that were moved, the intensity should start again as described above.

7.12 Subsequent days of Scrambler Therapy

7.121 Treatment will be administered using the above outlined principles of the recommended scrambler for 30 minutes of application time, on up to 10 consecutive weekdays as long as the patient has numbness/pain/tingling rating of more than 0 at the time they come in for treatment. This is

because without pain, there is no guidance to the provider about electrode placement. Subsequent treatments can rapidly be titrated up to the highest intensity tolerated during the previous treatment. Up to three days may be skipped to allow for weekends and holidays, if needed. Treatment must start on a Monday, Tuesday, or Wednesday; with the goal being 3 consecutive days of treatment before break (e.g. treatment cannot start Wednesday before Thanksgiving holiday weekend). The total of 10 treatments must be scheduled to be able to be completed within 16 calendar days).

- 7.122 The electrode placement may be modified on subsequent days, depending on how a patient responds to treatment.

7.2 Treatment Schedule for TENS arm

7.21 TENS Treatment Procedure

- 7.211 The patient will be given a new TENS machine that they will be able to keep. This unit will include a set of directions for use of this machine.
- 7.212 The study nurse will explain how to use the TENS machine, including a hands on learning session.
- 7.213 Written instructions will also be provided to the patient (Appendix XIV)
- 7.214 The patient will be instructed to use the TENS machine for 30 minutes per day, for 14 days, to address the area deemed most problematic (upper or lower extremities) of CIPN.
- 7.215 If the patient has questions during their 2 week treatment, they can call the study nurse.
- 7.216 The patient may also use the TENS on other areas of involvement (e.g. if their lower extremities are the main focus of the study, they may also treat their upper extremities).

7.3 Optional Substudies

7.31 Functional MRI (fMRI)

We plan to do fMRI on a subset of 12 patients, before Scrambler therapy and on the last planned day or two of treatment (± 1 day).

We will use the same approach have been used in the past for imaging experiments (Lebel, Becerra et al. 2008; Upadhyay, Knudsen et al. 2008; Upadhyay, Maleki et al. 2010). Subjects will be scanned on a HDxt 3.0T - 60cm TRM, Spectro (GE). During the MR session, subjects will be placed in the magnet for the experimental procedure and attached to various physiological monitoring apparatuses. During the experimental procedure, a series of standard anatomical images will be acquired. Once the anatomical images are completed, subjects will also undergo RSN (10 min), and DTI (10 min) imaging. The total estimated time the subject will be inside the magnet is 60 minutes. The imaging details are described below.

Anatomical Scans: We will use an established approach for imaging experiments. Subjects will be scanned on a 3.0T - 60cm TRM, Spectro (GE). We will acquire anatomical images using a magnetization prepared rapid gradient echo (MPRAGE) sequence (128 1.33mm-thick slices with an in-plane resolution of 1 mm (256x256)).

Resting State Scans (RSN): We will first obtain magnitude and phase images to unwarp functional scans; slice location, number, and thickness will be the same as those used in functional scans consisting of 41 slices with isotropic voxels (3mm) and 64x64 in-plane resolution. Then for RSN, we will generate images with a Gradient Echo EPI sequence (TR/TE = 2.5/30ms); 120 volumes will be collected per functional scan.

Diffusion Tensor Imaging (DTI): We will collect all DTI data using a single, shot-twice refocused echo planar pulse sequence at a 1.75 x 1.75 x 2.5 mm³ resolution. We will collect 8 single, non-diffusion weighted ($b = 0$ sec/mm²) volumes and 72, diffusion-weighted volumes with different gradient orientation at $b = 1000$ sec/mm² (TR = 7900 msec, TE = 92 msec, 5/8 partial Fourier, 3-fold SENSE acceleration). Fifty axial slices are sufficient to cover the entire cerebral cortex.

7.32 **mRNA blood testing**

mRNA blood testing will be done on a subset of 12 patients. Blood draws for CBC with differential and mRNA are completed at Baseline (prior to treatment) and on the last day or two of treatment (e.g., Day 9 or 10, if 10 treatments are given but sooner if earlier treatment completion is planned; ideally collected prior to treatment) (± 2 days).

For details on collection and processing see [Section 14.0](#).

7.33 **Audiovisual recording**

For patients receiving Scrambler therapy who agree to participate in the audiovisual recording portion of this current trial, the established procedures are outlined below:

- o An audio-video recording device will be placed in the treatment room prior to starting Scrambler Therapy. The device runs during the treatment and then is turned off.
- o A study assistant will upload video files to a secure server the day of each recording.
- o Files will be named "StudyID_Date" (MC15C1_3-2-2016) and placed in an "Original Recordings" folder.
- o Files will be converted to Audacity and WAV formats.
- o Recordings will be removed from the recorders following overnight backup on the specified research server.
- o Audio-video recording files will be deidentified (e.g. removal of names) using Audacity editing software.
- o After recordings have been de-identified, they will be converted to .WAV file type and stored for future review.

7.34 **Quantitative Sensory Testing (QST)**

We will do QST before Scrambler/TENS therapy and on the last day (± 3 days) of Scrambler/TENS therapy. We will only do this testing on patients that have lower extremity neuropathy as their major symptom (as opposed to upper

extremity neuropathy). We will obtain touch pressure and heat pain testing on both the dorsal foot and the lateral leg in 10 patients per study arm.

This testing will be ordered as a clinical test and paid for by research dollars.

Note: [REDACTED] is our contact person for ordering this test and the IRB number should be noted when ordering it.

7.4 Optional Crossover Continuation

7.41 Patients electing to crossover to the opposite treatment arm will be expected to complete an additional 2 weeks of treatment and 8 weeks of observation.

7.42 Substudies will not be offered for patients on crossover/continuation except by permission of PI.

8.0 Dosage Modification Based on Adverse Events

If a patient develops any substantial toxicity from the treatment (not expected), then treatment with either TENS or Scrambler therapy should be stopped.

9.0 Ancillary Treatment/Supportive Care

9.1 Full supportive care

Patients should, otherwise receive appropriate supportive care for their pain as clinically indicated.

9.2 Gabapentinoid use

Patients should not receive gabapentinoids (e.g. Neurontin®, Lyrica®) during treatment with Scrambler therapy. If patients are on gabapentinoids at the time of registration and are randomized to Scrambler therapy, they must be weaned off prior to receiving Scrambler therapy.

9.3 Other pain treatment

Other pain treatments are allowed if the pain is not satisfactorily controlled. All pain treatments and pain-related medications will be recorded.

9.4 Investigational agents

Concurrent use of investigational agents is not permitted unless preapproved by PI.

10.0 Adverse Event (AE) Reporting and Monitoring

10.1 Adverse Event Characteristics

CTCAE term (AE description) and grade: The descriptions and grading scales found in the revised NCI Common Terminology Criteria for Adverse Events (CTCAE) version 4.0 will be utilized for AE reporting. All appropriate treatment areas should have access to a copy of the CTCAE version 4.0. A copy of the CTCAE version 4.0 can be downloaded from the CTEP web site (<http://ctep.cancer.gov>).

10.11 Adverse event monitoring and reporting is a routine part of every clinical trial. First, identify and grade the severity of the event using a copy of the CTCAE v4.0. Next, determine whether the event is expected or unexpected (refer to Sections 10.12 and if the adverse event is related to the medical treatment or procedure (see Section 10.13). With this information, determine whether an adverse event should be reported as an expedited report (see Section 10.2) or as part of the routinely reported clinical data. **Important:** All AEs reported via expedited mechanisms must also be reported via the routine data reporting mechanisms defined by the protocol (see Sections 10.3).

Expedited and routine reports are to be completed within the timeframes and via the mechanisms specified in Sections 10.2 and 10.3. All expedited AE reports must also be sent to the local Institutional Review Board (IRB) according to local IRB's policies and procedures.

10.12 Expected vs. Unexpected

- The determination of whether an AE is expected is based on adverse event information provided in Section 10.3 of the protocol.
- Unexpected AEs are those not listed in the adverse event information provided in Section 10.3 of the protocol.

10.13 Assessment of Attribution

When assessing whether an adverse event is related to a medical treatment or procedure, the following attribution categories are utilized:

Definite - The adverse event *is clearly related* to the investigational agent(s).

Probable - The adverse event *is likely related* to the investigational agent(s).

Possible - The adverse event *may be related* to the investigational agent(s).

Unlikely - The adverse event *is doubtfully related* to the investigational agent(s).

Unrelated - The adverse event *is clearly NOT related* to the investigational agent(s)

10.2 Expedited Adverse Event Reporting Requirements

	Grade 4 or 5 Unexpected with Attribution of Possible, Probable, or Definite	Increased Incidence of an Expected AE ¹
FDA Form 3500 (MedWatch) within 10 working days ²	X	X

1. An increased incidence of an expected adverse event (AE) is based on the patients treated for this study at their site. A list of known/expected AEs is reported in the package insert or the literature, including AEs resulting from a drug overdose.
2. Submit form to the FDA, MedWatch, [name], by fax at [name] or online at <http://www.fda.gov/Safety/MedWatch/HowToReport/default.htm>.

Mayo Clinic Cancer Center (MCCC) Institutions: Attach copies to the Mayo Cancer Center SAE Reporting Form:

The MCCC Regulatory Affairs Unit (RAU) Risk Information Specialist will determine and complete IRB reporting. The RAU will submit to the MCCC SAE Coordinator.

- 10.3 Adverse events to be graded at each evaluation and pretreatment symptoms/conditions to be evaluated at baseline per the CTCAE v4.0 grading: NONE.
 - 10.31 Submit via appropriate MCCC Case Report Forms (i.e., paper or electronic, as applicable) the following AEs experienced by a patient and not specified in Section 10.3:
 - 10.311 Grade 2 AEs deemed *possibly, probably, or definitely* related to the study treatment or procedure.
 - 10.312 Grade 3 and 4 AEs regardless of attribution to the study treatment or procedure.
 - 10.313 Grade 5 AEs (Deaths)
 - 10.3131 Any death within 30 days of the patient's last study treatment or procedure regardless of attribution to the study treatment or procedure.
 - 10.3132 Any death more than 30 days after the patient's last study treatment or procedure that is felt to be at least possibly treatment related must also be submitted as a Grade 5 AE, with a CTCAE type and attribution assigned.

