2.2 Goal 2 Tolerability

Evaluate the tolerability of Scrambler therapy and compare it to TENS therapy, in this population.

Hypothesis 2: Scrambler therapy will be well tolerated and there will be no substantial differences in side effects between the Scrambler and TENS treatment groups.

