16.32 Secondary efficacy endpoints

Perceived treatment efficacy from the Subjective Global Impression of Change instrument (Appendix IXA and B) will be summarized (median and range for impression of change and frequency for preference) by arm and compared

(Wicoxon rank-sum test for impression of change and Chi-square test for preference) between treatment arms.

EORTC CIPN20 scores and changes in scores will be summarized (mean, sd, median, range) at each time point by arm and will be compared between arms using two-sample t-tests.

- 16.33 Goal: Evaluate the tolerability of Scrambler therapy and compare it to TENS therapy, in this population.

Frequency and type of toxicities occurred during therapy will be summarized by treatment arm and compared between arms using Fisher-exact test.

- 16.34 Goal: Evaluate whether Scrambler therapy, compared to TENS therapy, can decrease the use of pain medication for CIPN.

Type and frequency of analgesic used will be summarized by treatment arms and will be compared using Fisher-exact test.

- 16.35 Goal: Explore whether mRNA gene expression changes are similar to that previously reported by Starkweather et al.

In a descriptive manner, the gene expression will be compared to what was previously reported.

- 16.36 Goal: Explore whether Scrambler therapy will change fMRI.

Changes in fMRI following Scrambler therapy will be described in the subset of patients selected for this component of the study.

- 16.37 Descriptive statistics will be used for the data from Quantitative Sensory Testing.

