Appendix XB Daily TENS Treatment Log and Adverse Event Assessment

Initials _____
Study # _____
Date _____
Day _____

Patient Name: _____

Pain Area #1 _____

Cable 1 Max Setting: _____

Total Treatment Time: _____ (mins)

Pain Area #2 _____

Cable 2 Max Setting: _____

[figure not shown]
[figure not shown]
Total Treatment Time: _____ (mins)

Adverse Effect Assessment: Please note any adverse effects of treatment

Notes/Comments:

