Appendix XIII Principals of Positioning and Titrating Scrambler Treatment

Algorithm 1: Basic Scrambler Treatment Algorithm

Algorithm 2: Advanced Scrambler Treatment Algorithm
(If patient does not meet criteria for proper electrode placement)

Option 1: Reduce Area of Pain

Place all electrodes above area of pain

- For feet, place electrodes on leg above area of pain, most likely minimum of 2 electrode sets, but may use as many as fit and are tolerated, or pain/tingling is zeroed
- For hands, place electrodes on arm above area of pain, most likely minimum of 2 electrode sets, but may use as many as fit and are tolerated, or pain/tingling is zeroed

Goal: Replace pain or tingling with new/different tingling sensation in the area of pain, in order to reduce area of pain/tingling and allow for proper placement of electrodes in next session

Treat for 30 minutes after tingling begins

* Patient assessed daily for ability to follow Algorithm 1

Option 2: Treat in area of pain

When electrode cannot be placed in area of non-pain, an electrode can be placed in the area of **least** pain and then Algorithm 1 can be followed

However, this can cause increased pain and discomfort and therefore this technique should be used based on provider experience and patient tolerability

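### Low-grade side effects noted on the daily treatment logs have no specified route into the Goal 2 tolerability comparison, and a non-significant test on the remaining events would not support Hypothesis 2

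*Combined protocol and SAP*

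**What the plan says.** - **Hypothesis (Section 2.2).** "Scrambler therapy will be well tolerated and there will be no substantial differences in side effects between the Scrambler and TENS treatment groups". No margin defines a substantial difference.
- **Analysis (Section 16.33).** "Frequency and type of toxicities occurred during therapy will be summarized by treatment arm", with a Fisher exact test between arms. The section gives no grade threshold, data source or coding rule.
- **Routine reporting (Sections 10.11, 10.3 and 10.31).** Events that are not expedited go through the routine route. Section 10.3 reads "pretreatment symptoms/conditions to be evaluated at baseline per the CTCAE v4.0 grading: NONE", and the same line covers events graded at each evaluation. Section 10.31 then requires "Grade 2 AEs deemed *possibly, probably, or definitely* related to the study treatment or procedure", "Grade 3 and 4 AEs regardless of attribution to the study treatment or procedure", and specified deaths. Grade 1 is not listed.
- **Daily logs (Appendix XA and XB).** Both are scheduled daily in Section 4.0 and ask for effects of any severity. The TENS log reads "Adverse Effect Assessment: Please note any adverse effects of treatment". Neither has a field for grade or attribution.
- **Foreseen effects.** Section 7.113: "If a patient develops pain or a burning sensation with any of the electrodes, then the treatment should be interrupted". Appendix XIII, on placing an electrode within the painful area: "However, this can cause increased pain and discomfort".
- **Submission timetable (Section 18.12).** It names an Adverse Event form and the patient questionnaires, but not the Appendix X log.

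**The concern.** The two treatments differ in how strongly they are felt. Scrambler is raised to the strongest level the patient can bear (Section 7.113). TENS is set to a level that is felt and comfortable (Appendix XIV). If the arms differ in tolerability, mild local effects are a plausible place for it to show. The only written rule for carrying routine adverse events into the trial data leaves out grade 1.

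Hypothesis 2 predicts good tolerability and no substantial difference. A comparison restricted to related grade 2 and higher events could come out non-significant because little was counted, and that result would look like confirmation.

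**Working it through.** **1. Tracing a mild effect.** Suppose a patient in either arm has a mild burning sensation under an electrode.
- Section 4.0 with Appendix XA or XB: it can be written on the log as free text.
- Section 11.2: adverse events are evaluated with CTCAE criteria, so it could be graded.
- Section 10.31: if it is grade 1, no entry on the adverse event form is required.
- Section 18.12: the log is not a named submission.
- Section 16.33: the analysis does not say whether it uses the form, the logs or both.

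The effect can be recorded, but no stated step takes it to the comparison.

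**2. The plan's own figures.** The documents give none for tolerability. Table 16.51 concerns the efficacy responder endpoint. It reproduces with a one-sided pooled normal approximation (80.7, 80.4, 81.7, 81.3 and 82.1% against the stated 80, 80, 81, 81 and 82%), but it has no bearing here.

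**3. What the Fisher test needs.** Inputs: 25 per arm (Section 16.5) and the Fisher exact test (Section 16.33). A two-sided 0.05 level is assumed, because Section 16.33 states none. With b affected patients in one arm and none in the other, p = 2 × C(25,b)/C(50,b).
- b = 4: 2 × 12,650/230,300 = 0.110
- b = 5: 2 × 53,130/2,118,760 = 0.0502
- b = 6: 2 × 177,100/15,890,700 = 0.022

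At least 6 v 0 is needed, that is 6/25 = 24% v 0%. A one-sided 0.05 test halves these values (0.055 at 4 v 0, 0.025 at 5 v 0) and would need 5 v 0.

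**4. What an empty arm allows.** For 0 of 25, the exact two-sided 95% upper limit is 1 − 0.025^(1/25) = 13.7%, or about one patient in seven.

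**5. Power over a range of assumed rates.** The documents supply no rates, so every row is an assumption (exact two-sided Fisher power, 25 per arm).

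| Assumed rates | Power |
|---|---|
| 0% v 8% | 1.2% |
| 4% v 12% | 3.5% |
| 4% v 20% | 23% |
| 5% v 30% | 55% |
| 5% v 40% | 82% |

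If the counted events are uncommon, the test can hardly reject. If mild effects are counted and are common and unequal, it has a reasonable chance. Which row applies is unknown.

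**The case against.** A reader might infer that mild effects can never reach the comparison. The documents do not support that. Section 16.33 sets no grade floor and does not tie itself to Section 10.31. Both logs ask for any effect. TENS patients are called on Day 2 and once on Day 8-10 about toxicities, and weekly follow-up calls record reported events. Pain, tingling and numbness are rated after each session (Appendix VI), and Appendix IX asks whether symptoms are worse, so added pain in the treated area could show there. Local skin effects elsewhere might not.

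A reader might also infer that the table will be almost empty, citing the two earliest reports in Section 1.4, which stated no adverse effects. Those reports concern Scrambler only, in other pain conditions, and refer to effects of any grade. They give no rate of grade 2 or higher events in CIPN and none for TENS.

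Nor does any section assign a grade to the stinging, burning or discomfort. That they are mostly grade 1 is a reasonable inference, since burning is handled by interrupting treatment and moving the electrode, but it is not stated. Stinging is also a titration cue for Scrambler, so counting every sensation could inflate that arm alone.

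Finally, tolerability is not the primary endpoint, and Section 16.5 says the study is not confirmatory.

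These points limit the claim but do not remove it. Capture on a log is not submission or analysis, and Section 10.31 as written filters out grade 1.

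**Conclusion.** The concern holds as a gap between collection and analysis. Low-grade treatment effects are asked for daily in both arms, but they have no specified path into the Goal 2 comparison. How much would be lost cannot be computed, because the documents give no adverse event rate for this setting.

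What can be stated is the weakness of the planned test. At 25 evaluable patients per arm, counting each patient once and testing two-sided at 0.05, significance requires at least 6 v 0. An arm with no events remains compatible with a true rate up to 13.7%. With no margin in Section 2.2, a non-significant Fisher test on grade 2 and higher events would not establish Hypothesis 2. This should be changed, although it does not affect the primary endpoint.

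**What to change.** - **Section 10.31:** also require submission of treatment-related adverse effects of any grade recorded on Appendix XA or XB, each with its CTCAE grade.
- **Section 16.33:** name this as the source. Compare the proportion of patients with any treatment-related adverse effect of any grade. Report per-patient incidence by arm and the difference, with confidence intervals, and do not read a non-significant test as evidence of no difference.
- **Patient booklet:** put the same patient-answered daily adverse-effect question in both arms. Treatment-period calls are specified for TENS patients only, so the present sources differ between arms.
- **Definition:** state that sensations elicited only as titration cues are not counted.

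The cost is one booklet item and more low-grade rows to enter and code. Expedited reporting and the stopping rules need not change. Some difference in ascertainment will remain between attended Scrambler sessions and self-administered TENS, and the report should say so.
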